8.2 Secondary Safety Endpoints

8.2.1 Major or non-major clinically relevant bleeding through Day 30

The frequency and percentage of participants with major or non-major clinically relevant bleeding through Day 30 as adjudicated by the CEC will be presented by each rNAPc2 dose and heparin dose (pooled and via characteristics, i.e., Prophylactic vs. Therapeutic, Unfractionated vs Low Molecular Weight).

8.2.2 Any bleeding through Day 8 and through Day 30

The frequency and percentage of participants with any bleeding major, non-major clinically relevant, non-major and not clinically relevant as defined in the protocol) through Day 8 and through Day 30 will be presented by each rNAPc2 dose and heparin dose (pooled and via characteristics, i.e., Prophylactic vs Therapeutic, Unfractionated vs. Low Molecular Weight).

8.2.3 Other Adverse Events

Safety assessments will also include monitoring of serious adverse event(s) (SAE) and non-serious adverse event(s) (AE). Efficacy and safety endpoints that are adjudicated positively as study outcomes, including all bleeding events, will not be considered as AEs or SAEs.

All AEs will be collected from the time of randomization until the participant completes Day 30 or final contact, whichever is longer. All SAEs will be collected from the time of consent until the participant completes Day 30 or final contact, whichever is longer.

All reported AEs will be coded using the Medical Dictionary for Regulatory Activities (MedDRA).

Participant counts will be summarized using frequencies and percentages. A participant will be counted only once per category of summarization (e.g., if a participant has multiple AEs, the participant will only be counted once in the overall 'Any AE' row and will be counted once in each row for the specific AE category reported). Where participants have more than one level of severity/relatedness recorded only the highest level of severity/relatedness will be summarized.

Participant counts will be summarized by system, organ class and preferred term (PTm) by treatment group for treatment-emergent AEs (TEAEs) and by seriousness, relatedness.

An AE identified by the investigator as 'Related' or 'Potentially Related' or where relationship is missing will be considered 'related to study treatment.'

All AEs will be listed. Listings of SAEs, Related AEs, fatal and AEs of special interest (e.g., Overdose, misuse, or accidental exposure to study drug; medical error involving study drug), will also be listed. Additional details of SAEs and Deaths will also be listed.

Treatment Emergent is defined as any SAE/AE that has a start date during or after administration of the investigational product (i.e., randomized rNAPc2 or heparin treatment), post-randomization up to Day 30 or final contact.

Data will be displayed as collected in the clinical database. Adverse Events with missing start dates will be considered as treatment emergent.

8.3 Laboratory Data

A summary of laboratory (Central Laboratory) values (e.g., AST, ALT and bilirubin) outside normal limits (i.e., either above the ULN or below the lower limit of normal (LLN) where limits are defined), as well as a summary of any participant potentially meeting the criteria for Hy's law will be provided where Hy's Law criteria will be defined as: AST or ALT > 3× ULN and total bilirubin > 2× ULN at any time during the study.

9 Interim Analyses

Additional details of these analyses will be described in the DSMC Charter.

10 Composite and Net Endpoints

Composite endpoints will first be analyzed as an aggregate and then component-wise, as discussed in the context of modeling clinical events in [Section 7.2.3](#). The primary approach to net outcomes will be to perform them in all randomized patients in the 30-day study period.

Composite/net clinical outcomes include the combination of irreversible harm and efficacy outcomes, including:

- All-cause mortality, thrombotic events, initiation of organ support, rehospitalization adjudicated as to its relatedness to COVID-19.

11 Subgroup and Sensitivity Analyses

The sensitivity analyses will be performed on the ITT, mITT, and Per Protocol populations.

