5.1 & 5.3	
 Added language requiring male patients to avoid partner pregnancy and sperm donation 	
 In agreement with regulatory agency request
8.1.2	
 Removed central laboratory assessment of AST, ALT and bilirubin 	
 Remove duplication of laboratory assessments in line with standard of care site COVID-19 practices
8.5	
 Removed Unanticipated Problem Section and Unanticipated Problem Reporting Section 	
 These sections did not inform clinical trial execution for ASPEN-COVID-19
9.0	
 Increase to study sample size Addition of an interim efficacy analysis and removal of Unblinded Review Committee Clarification that primary endpoint analysis will evaluate proportional changes in D-dimer at Day 8; to be detailed in the statistical analysis plan 	
 Given the evolution of COVID-19 management since the start of ASPEN-COVID-19, the original rNAPc2 sample size and treatment effect assumptions were updated in order to increase experience in a diversity of COVID-19 patients. Changes in COVID-19 management that were considered include 1) evolving evidence for standard of care, 2) widespread use of several COVID-19 therapies of proven

		benefit, and 3) changes in background therapy.
--	--	--

Protocol Amendment History

Version	Date	Description of Change	Brief Rationale
2.00	28Aug2020	Design adjustments prior to study initiation	Incorporate feedback
3.00	16Sep2020	Administrative adjustments prior to study initiation	Ensure consistency and clarity throughout the protocol
4.00	28Oct2020	Adjustments prior to study initiation	Incorporate feedback
5.00	01Feb2021	Update to endpoints and revision of laboratory assessments; Clarification on requirements for women of child-bearing potential and safety reporting	Scientific revision of endpoints; safety clarifications
6.00	07Jul2021	Clarification of some inclusion/exclusion based on regulatory agency review; increase of study sample size	Given the evolution of COVID-19 management since the start of ASPEN-COVID-19, the original rNAPc2 sample size and treatment effect assumptions were updated in order to increase experience in a diversity of COVID-19 patients

Protocol Approval Signature:

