8 STUDY ASSESSMENTS AND PROCEDURES

8.1 STUDY PROCEDURES

8.1.1 SCHEDULE OF ACTIVITIES

Table 2a. Schedule of Activities (SoA)

Activity	Screen Day -7 to 1	Baseline Day 1	Day 2 (24h post-dose \pm 2h)	Day 3 \pm 1d	Day 5 \pm 1d	Day 8 \pm 1d	Day of Hospital Discharge	Day 30 \pm 3d
Informed consent	x							
Assess eligibility	x	x						
Randomize		x						
Medical history (COVID-19, cardiovascular, medical/ surgical history) ^b		x						
Concomitant medication ^b		x	x	x	x	x	x	x ^d
Baseline demographics ^b	x							
Focused physical examination, vital signs, weight, height ^b		x						
Study medication ^c		rNAPc2 7.5 μ g/kg SC on Day 1 and 5 μ g/kg SC on Days 3 and 5 or rNAPc2 5 μ g/kg SC on Day 1 and 3 μ g/kg SC on Days 3 and 5 or heparin per SoC						
Local laboratory values	x ^a	Record values of interest performed in the hospital clinical laboratory until hospital discharge or day 30 visit (whichever is first). In the case where a lab test is measured multiple times per day, the first scheduled values as well as any additional values that represent a clinically significant change should be reported.						
Assess need for inpatient medical services & complete ACTT			Daily until discharged to outpatient status or death or Day 30 reached					
Clinical & adverse events ^g	x	x	x	x	x	x	x	x ^d
Post-COVID functional status (PCFS) scale							x ^h	x ^d
Vital status								x ^d
Healthcare utilization							x	x ^d
Central Laboratory assessments (see Table 2b)		x	x	x ^e		x ^f	x ^f	x ^e

^a Local lab D-dimer drawn during hospitalization and prior to randomization will be used for eligibility and randomization stratification

^b May be obtained/extracted from medical record to minimize staff exposure to COVID-19

^c rNAPc2 must be dosed on Days 1, 3 and 5; only one rNAPc2 dose regimen is anticipated in Phase 3; Participants randomized to receive heparin will have doses administered per standard of care (SoC)

^d Participants who are discharged prior to Day 30 may have these activities performed remotely

^e For phase 2b only

^f If participant is discharged prior to Day 8, central laboratory assessments should be performed at hospital discharge

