8.1.2 LABORATORY SAMPLES AND VALUES

Participants will have laboratory samples collected and analyzed both locally and centrally in accordance with the SoA.

Local Laboratory Values

Laboratory tests of interest listed below, obtained via the local laboratory that are used to assess eligibility*, or are collected during the participant's enrollment until hospital discharge or Day 30 visit (whichever is first) should be reported via the eCRF. In the case of D-dimer, initial value (eligibility) is preferred as collected at the time of hospital admission, prior to initiation of heparin treatment. In the case where a lab test is measured multiple times per day, the first scheduled values as well as any additional values that represent a clinically significant change should be reported.

- Hemoglobin
- D-dimer*
- White blood cell count (WBC)
- Platelet count*
- Estimated glomerular filtration rate (eGFR)*
- Aspartate aminotransferase (AST)
- Alanine aminotransferase (ALT)
- Total bilirubin
- Prothrombin time (PT)
- Partial thromboplastin time (PTT)
- Troponin
- Brain natriuretic peptide (BNP)

Central Laboratory Sample(s)

Central laboratory samples should be collected and shipped to the central laboratory as described in the Laboratory Manual. The following table outlines the samples that will be collected and analyzed via the central laboratory.

Table 2b. Central Laboratory Blood Collection

Day 1 ^a	Day 2 (24h post-dose)	Day 3 Phase 2b only	Day 8 ^b , or Day of Hospital Discharge (if prior to Day 8)	Day 30 Phase 2b only
Samples for clinical laboratory tests				
IL-6, hsCRP			IL-6, hsCRP	
D-dimer, PT, PTT, factor Xa tissue factor, antiphospholipid antibody	D-dimer, PT, PTT	D-dimer, PT, PTT	D-dimer, PT, PTT, factor Xa tissue factor, antiphospholipid antibody	antiphospholipid antibody
ADA for rNAPc2 subjects (Phase 2b only)	PK sample for rNAPc2 subjects (Phase 2b only)		PK sample for rNAPc2 subjects (Phase 2b only)	ADA for rNAPc2 subjects
Samples for future research use^c				
Future use serum and plasma aliquots and buffy coat			Future use serum and plasma aliquots	

^a Baseline Central Laboratory sample should be collected before administration of study medication (rNAPc2 or heparin). A sample up to 1-hour post-administration is acceptable.

^b For rNAPc2-allocated participants, Day 8 Central Laboratory samples should be collected before that day's dose of SoC thromboprophylaxis, if prescribed.

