9.4 STATISTICAL ANALYSES

9.4.1 GENERAL APPROACH

The statistical analyses described in this section will be performed as further detailed in a separate statistical analysis plan. The statistical analysis plan will supersede the protocol in the event of any differences between the two documents in the plans for data analysis, and the protocol will be amended if appropriate. The statistical analysis plan will be included as an appendix in the clinical study report for this protocol.

Descriptive statistics for continuous variables will include the number of participants, mean and standard deviation, median, first and third quartiles, and minimum and maximum values. Descriptive statistics for categorical variables will contain count and percentage.

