9.4.4 SAFETY ANALYSES

Incidence rates of AEs including adjudicated bleeding events, all, serious, fatal, severe and treatment-related AEs reported throughout the conduct of the study will be tabulated by preferred term and system organ class.

Changes in laboratory values and vital signs will be summarized with descriptive statistics. The incidence of concomitant medications will also be summarized.

Drop in hemoglobin level as reported per local laboratory data will be used as an indicator of potential bleeding risk.

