7.3.3	Post-COVID Functional Status.....	21
7.4	Significance.....	21
8	Safety Analysis	21
8.1	Primary Safety Endpoint	21
8.2	Secondary Safety Endpoints.....	22
8.2.1	Major or non-major clinically relevant bleeding through Day 30	22
8.2.2	Any bleeding through Day 8 and through Day 30	22
8.2.3	Other Adverse Events	22
8.3	Laboratory Data.....	23
9	Interim Analyses.....	23
10	Composite and Net Endpoints	23
11	Subgroup and Sensitivity Analyses	23
11.1	Primary Efficacy Endpoint Sensitivity Analysis.....	23
11.2	Primary Efficacy Endpoint Subgroup Analyses.....	23
11.3	Secondary Efficacy Endpoint Subgroup and Sensitivity Analyses	24
11.4	Additional Safety Analyses	24
12	Changes from Methods Planned in the Protocol	24
13	References.....	24
14	Appendix.....	25
14.1	COVID Severity Definitions	25
14.2	Descriptions of the Models and Methods Used.....	25
14.2.1	Bayesian Description	25
14.2.2	MI Description	25
14.2.3	Power Description.....	25

Approvals

Signatures		
Biostatistician (ARCA)	_____ [name]	_____ Date
Biostatistician (CPC)	_____ [name]	_____ Date
Principal Investigator	_____ [name], MPH	_____ Date
Chief Scientific Officer (ARCA)	_____ [name], PhD	_____ Date

Revision History

VERSION	DESCRIPTION OF CHANGE
1.0	Original
2.0	
 • Inserted language submitted in IND 150187, Sequence 0015 on 29 Nov 2021 containing Sponsor’s response to the Division’s review of Version 1.0 clarifying Wilcoxon Signed Rank will not be used in the primary efficacy endpoint analysis. • Added composite of clinical events as a secondary efficacy endpoint in Section 2.5.1. • Moved probability of discharge as assessed by ACTT from exploratory efficacy endpoint to secondary endpoint in Section 2.5.1 • Added multiplicity control description to Section 5.7 • Added Section 5.8 Transformations and Normality • Added Section 7.1.2 Secondary Analysis of the Primary Efficacy Endpoint • Added Section 7.2.3 Composite of Clinical Events • Added Section 10 Composite and Net Endpoints • Added Section 11 Subgroup and Sensitivity Analyses to provide additional description of how types of missingness will be addressed via multiple imputation. • Added Section 14.2 Description of Models and Methods which include descriptions of the Bayesian models, methods for multiple imputation, and methods for power analysis used in this study. • Added Section 12 Changes from Methods Planned in the Protocol to describe the key changes in either endpoint or analysis methodology.

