3.1 Database Description

The following data sources will be used to create the final study tables, figures, and listings (TFLs).

- Protocol Deviation database which will store protocol deviations
- Clinical Endpoint Adjudication database which will store all adjudicated review fields and outcomes
- Central laboratory data from PPD
- Clinical database which will store all other data used for analysis

These databases are hosted by the following systems:

- Protocol Deviation database: DATATRAK UX CTMS
- Adjudication database: AG Mednet
- Central lab data from PPD transferred to CPC as SAS dataset
- Clinical database: DATATRAK UX EDC™

Separate data management and adjudication plans will describe the set-up and management of these databases including preparing and selecting data for study analysis. The adjudication, laboratory and clinical databases will be reconciled to ensure within- and cross-form consistency.

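### SAP 8.3 takes out-of-range AST, ALT and bilirubin from the central laboratory, but the current protocol collects them only locally; a lesser point is that the CMH test in SAP 11.4 has no usable stratifier named

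*SAP*

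**What the plan says.** **Liver tests.** SAP 8.3 describes "A summary of laboratory (Central Laboratory) values (e.g., AST, ALT and bilirubin) outside normal limits". The same sentence adds a summary of potential Hy's law cases (AST or ALT above 3× ULN with total bilirubin above 2× ULN), without saying which laboratory supplies the values.

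Protocol 8.1.2 has two lists. The local list includes "Aspartate aminotransferase (AST"), ALT and total bilirubin. The central list, Table 2b, has none of them. The Schedule of Activities describes the local values this way: "Record values of interest performed in the hospital clinical laboratory until hospital discharge or day 30 visit (whichever is first"). They are therefore whatever routine care produces, not scheduled study tests.

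Protocol 9.4.4 sets no source limit: "Changes in laboratory values and vital signs will be summarized with descriptive statistics". Protocol 9.4.1 adds: "The statistical analysis plan will supersede the protocol in the event of any differences between the two documents in the plans for data analysis". SAP 12, which lists departures from the protocol, does not mention laboratory source.

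**Haemoglobin.** SAP 11.4 turns the local haemoglobin decrease into a yes/no event at 3 g/dL. It treats heparin patients as one group, stratifies rNAPc2 patients by regimen received, and then calls for a stratified Cochran-Mantel-Haenszel (CMH) test across two treatment groups. It names no stratum that both groups share.

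**The concern.** SAP 8.3 sends the programmer to a dataset that, under the current protocol, does not contain the tests it gives as examples. SAP 3.1 keeps the central laboratory transfer separate from the clinical database, so the label decides which file is opened. The values that do exist could be left out of the liver table, and the Hy's law screen would depend on whichever source the programmer picks.

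In SAP 11.4 the question is whether the test can be run and reproduced as written. A stratified comparison of two arms needs strata that contain patients from both arms. Regimen of rNAPc2 cannot supply them.

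**Working it through.** **1. Liver tests: the two current texts side by side**

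| Central draw (Table 2b) | Tests | AST, ALT or bilirubin? |
|---|---|---|
| Day 1 | IL-6, hsCRP, D-dimer, PT, PTT, factor Xa, tissue factor, antiphospholipid antibody, ADA | No |
| Day 2 | D-dimer, PT, PTT, PK | No |
| Day 3 | D-dimer, PT, PTT | No |
| Day 8 or discharge | IL-6, hsCRP, D-dimer, PT, PTT, factor Xa, tissue factor, antiphospholipid antibody, PK | No |
| Day 30 | antiphospholipid antibody, ADA | No |

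Liver tests appear in 0 of 5 central draws. The local list has 12 tests, of which 3 are AST, ALT and total bilirubin. Only D-dimer, platelet count and eGFR carry the eligibility asterisk, so a baseline liver value is not guaranteed.

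**2. Could the SAP simply be older than the protocol change?** No. The V6.00 (07Jul2021) change list records: "Removed central laboratory assessment of AST, ALT and bilirubin". That entry explains where the mismatch comes from and agrees with Table 2b; the inconsistency itself lies between the current SAP and the current protocol. The SAP revision history for version 2.0 reads: "Inserted language submitted in IND 150187, Sequence 0015 on 29 Nov 2021". Versions 2.0 and 3.0 therefore both follow V6.00, and 8.3 still carries the central label.

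**3. Where the values are.** SAP 3.1 lists, beside the central transfer, a "Clinical database which will store all other data used for analysis". Local values entered in the eCRF belong there. The data exist, but 8.3 points elsewhere.

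**4. CMH test with regimen as the stratum.** For each stratum, let a be rNAPc2 events, n1 and n0 the rNAPc2 and heparin patients, m total events and N total patients. The numerator term is a − n1·m/N and the variance term is n1·n0·m·(N − m)/(N²(N − 1)). The arms are 160 split 1:1:2, or 40/40/80. The event counts below are illustrative assumptions.

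- Lower dose only, 4 events of 40: 4 − 40·4/40 = 0; n0 = 0, so variance 0.
- Higher dose only, 6 of 40: 6 − 40·6/40 = 0; n0 = 0, so variance 0.
- Heparin only, 8 of 80: 0 − 0·8/80 = 0; n1 = 0, so variance 0.

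The statistic is 0/0 whatever the counts, because each stratum holds one arm only.

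**5. Two ways round it** (simulated, no true difference, two-sided 5%; the documents give no rates for this event, so rates are assumed)

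- Reuse all 80 heparin patients against each dose: 2 × (40 + 80) = 240 patients analysed from 160. Type I error is 9.3%, 8.6% and 9.0% at event rates of 5%, 10% and 20% (200,000 replicates).
- Stratify pooled rNAPc2 versus heparin (80 versus 80) by D-dimer stratum: type I error is 4.3% to 5.1% over overall event rates p of 5% to 30%, with 1.3p and 0.7p in the high and low strata and 30%, 50% or 70% of patients in the high stratum (100,000 replicates).

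**6. Boundary.** An event is a fall of more than 3 g/dL and a non-event a fall of less than 3 g/dL. A fall of exactly 3 g/dL is in neither.

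**The case against.** The strongest reply is that no data are lost. AST, ALT and total bilirubin are reported in the eCRF, protocol 9.4.4 does not restrict laboratory summaries to central values, and the central label is one outdated parenthesis that a careful programmer would query. The supersession clause in protocol 9.4.1 covers plans for analysis and cannot create samples nobody draws. The table is descriptive, the protocol's listed risks (section 2.3.1) name no liver signal, and adverse events are collected separately. All of this limits the consequence. It does not make the label right: the SAP names its sources deliberately elsewhere (paired central or local D-dimer in 7.1.1, local haemoglobin in 11.4), and 9.4.1 gives a reader no ground for setting 8.3 aside.

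A reader might infer more than the documents support:

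- *That Hy's law screening is confined to central values.* The clause names no source and covers any time during the study, so local values are not barred. Any calculation of how weak a central-only screen would be models a rule the SAP does not state.
- *That a known share of the 160 participants would be missing from the table.* The documents do not give enrolment by protocol version, so no share can be derived.
- *That the CMH test is invalid.* The regimen sentence in 11.4 can be read as describing how groups are displayed, with the trial's D-dimer stratification intended for the test. On that reading the test works. But SAP 5.4 applies that stratum only where an analysis indicates it, and 11.4 does not, whereas 7.2.2 names its stratifier. What remains is an unnamed variable in a supplementary test.

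**Conclusion.** The main point holds. SAP 8.3 states a source that the current protocol no longer supplies for AST, ALT and bilirubin (0 of 5 central draws), and SAP 12 does not disclose a change. This is an error in the text, not merely missing detail. Its effect is limited to the liver rows for participants enrolled under V6.00 and to an unspecified source for Hy's law; summaries of tests that are still central are unaffected. The size rests on Table 2b alone and needs no assumption about enrolment.

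The CMH point is minor. With the only stratifier named, the statistic is undefined; with the D-dimer stratum it behaves properly under the assumed event rates. The 3 g/dL boundary is a small gap.

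Neither point affects the primary endpoint or the adjudicated bleeding tables. Both should be corrected.

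**What to change.** **SAP 8.3.** Name the local eCRF values of AST, ALT and total bilirubin as the source for both the out-of-range and the Hy's law summaries, together with any central values from earlier enrolees. Judge local values against the local reference range where it is captured. Report the number of participants per arm with at least one post-baseline value, so that an absence of cases can be read against the number tested.

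**SAP 11.4.** State that the rNAPc2 versus heparin CMH test is stratified by the randomization D-dimer stratum (above, or at or below, 2× ULN). Keep the display by rNAPc2 regimen; any per-dose comparison is the sponsor's choice, but should be stated. Assign a fall of exactly 3 g/dL to one category.

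**Cost.** No new samples. If sites' reference ranges for the three liver tests are already captured, the change is SAP wording and programming. The documents do not confirm that they are; if not, sites must supply them. Local tests are unscheduled and less standardized than central ones, and some participants may have no baseline or follow-up value, which is why the denominators need to be shown.
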